7.2. Subject Follow up and Protection against Risk

All subjects will be given [name] contact number and encouraged to report any concerns and complications during the 8-day study period and following completion of the study. In the unlikely event that acupuncture causes lasting discomfort, bothersome ecchymoses, worsening of carpal tunnel and neuropathy symptoms, [name] will be available for urgent assessment and treatment. If the patient needs further neurologic or other care, they will be referred to [name] clinic or to one of the other providers in the neuromuscular division or another appropriate clinician within OHSU. The informed consent will clearly state that a subject may discontinue participation in the study at any time.

As with all human subject investigations at OHSU, any adverse events will be reported to the IRB and there is a Data and Safety Monitoring Plan in place (see details below).

7.3. Adverse Event Tracking and Reporting - Data and Safety Monitoring Plan

There is a Data and Safety Monitoring Plan (DSMP) in place for the IRB-approved study "Local effects of acupuncture on the Median and Ulnar nerves in patients with Carpal Tunnel Syndrome", in accordance with OHSU IRB's recommendations and guidelines.

According to this IRB-approved DSMP, an independent study safety monitor has been appointed – [name]. The independent monitor is a neuromuscular expert and has no conflict of interest and no direct involvement in the study. The research staff will report any unanticipated problems and adverse events to the PI and the independent monitor. The PI will be responsible that the study procedures follow the approved protocol.

The independent monitor will receive a monthly safety report prepared by [name]. The report will include information on any adverse events, unanticipated problems and protocol

deviations that have occurred each month. Reportable unanticipated adverse events include: infection at the acupuncture needling site, moderate-severe bruising and bleeding at the acupuncture site, moderate-severe pain and discomfort after acupuncture, new onset of weakness or numbness, permanent worsening of carpal tunnel syndrome symptoms and any other adverse events. Additionally, serious adverse events such as death, life-threatening adverse events, inpatient hospitalization, persistent or significant disability/incapacity will be immediately reported to [name] and to the IRB. Unanticipated adverse events, as well as inability to tolerate experimental procedures will result in immediate exit from the study.

Unanticipated problems will be reported in accordance with the OHSU procedures and timeframes - within 7 calendar days in case of death and life-threatening events or within 15 calendar days for all other adverse events or unanticipated problems.

8. INTERVENTION DISCONTINUATION

A subject may withdraw consent at any point in the study, as stated in the OHSU Consent-and-Authorization Form. Other reasons for exiting the study include inability to comply with QST due to a cognitive problem, inability to tolerate QST or NCS, inability to tolerate acupuncture or electroacupuncture.

In general, since this is a brief study with only 2 visits, we do not anticipate that many subjects will exit the study. Should a subject exit the study, his/her data will be included in the analysis.

9. STATISTICAL CONSIDERATIONS

9.1. Sample Size Calculation

A mechanistic study of acupuncture, which examines its local, nerve-specific effects using Quantitative Sensory Testing (QST) and Nerve Conduction Studies (NCS) as outcome measures has not been attempted before. Therefore, we estimated acupuncture's effects based on larger studies drawn from the literature. Changes in acupuncture-associated sensation were derived from Lang et al (42) - an evaluation of manual and electroacupuncture- induced analgesia in the legs, using 24 healthy subjects, 12 men and 12 women, in a cross-over design. Effect sizes in Median nerve conduction velocity (NCV) were calculated as clinically relevant changes from the mean NCV reported by Kimura et. al (52) and Di Guglielmo et. al (53). Both studies were NCS characterizations specifically in CTS with 105 and 198 patients respectively and publicized in the AAEM summary statement on electrodiagnostic parameters in CTS (54).

QST testing from the Lang et al (42) acupuncture intervention was observed to be a significant predictor of Cold Detection Threshold (CDT), with a 0.2°C change ($-3.6 \pm 0.9^{\circ}\text{C}$ to $-3.4 \pm 0.4^{\circ}\text{C}$) seen in the low-frequency-acupuncture treated legs. As this study was conducted in healthy subjects, we expect to see a greater effect of acupuncture on patients with neuropathy, especially as the acupuncture will be administered locally, with greater potential to affect the underlying nerve. Sample size estimation assumed the variance of the change in QST outcomes due to local acupuncture delivery over the Median and Ulnar nerves will be comparable to the variance in QST observed by Lang after acupuncture in healthy nerves ($\sigma^2_{\text{CDT}} = 0.696 (^{\circ}\text{C})^2$). Under these assumptions, a minimum QST change of 0.35°C , considered reasonable as an on-treatment effect

size in CDT, would be observed as statistically significant at a significance level of $\alpha=0.05$ with 80% power with 20 subjects per arm.

The pooled parameters of the studies by Kimura et al (52) and Di Guglielmo et al (53) observed a mean Median nerve motor NCV of 47.5 ± 5.76 m/s in their combined cohort of 303 CTS patients. At minimum and assuming the same variance as seen historically ($\sigma^2_{\text{NCV}} = 33.2$ (m/s)²), an 8% change in NCS (corresponding to a clinically feasible 3.7 m/s change post-intervention) would be considered significant with the same arm size of 20 subjects and at the same significance of $\alpha=0.05$ and 80% power.

Although estimated from the literature, these on-treatment effect sizes are considered reasonable based on previously collected pilot data in three subjects. When treatment and testing location were matched, a 0.337°C increase in CDT was observed in the Median nerve compared to the Ulnar nerve. Similarly, a Median nerve motor NCV improvement of 3.3 m/s was observed in the wrist. These initial pilot values are encouraging as they agree well with projected on-treatment effect size estimates from the literature.

Specific Aim 1: We expect that the proposed sample size of 20 per acupuncture modality will enable us to see significant treatment-dependent changes in the NCS and QST (CDT, VDT) of the diseased Median nerve within each of the 3 intervention systems (MA, LF-EA, HF-EA).

Specific Aim 2: For the current study, the Ulnar nerve is serving as a healthy control to allow for comparison to the diseased Median nerve post-intervention. Historic studies measuring the local, direct effect of acupuncture on a healthy nerve or studies comparing the local effects of acupuncture on a healthy versus a diseased nerve are not available. With respect to our Specific Aim 2 hypothesis, the Ulnar nerve is serving as a disease-free control condition, wherein acupuncture-dependent change in QST and NCS in the Ulnar nerve is anticipated to be largely negligible as the nerve is already functioning at optimal physiologic parameters. Due to this expectation of negligible treatment effect in the Ulnar nerve, the proposed sample size from Specific Aim 1 (20 subjects per acupuncture modality) is expected to be sufficient for these comparisons within each type of acupuncture. Further, we plan to carry out the Median/Ulnar nerve comparisons separately for each of the 3 intervention modalities. The use of both Median and Ulnar nerves lets the treatment as well as control conditions of interest come from the same subjects, allowing them to serve as their own controls. However, this repetition design warrants the use of mixed-model analysis so the random-effects portion can account for the intra-subject serial correlation expected with repeated measurements.

Specific Aim 3: With regards to the proper sample size for comparison among the 3 types of acupuncture – we based the sample size calculation for each study arm in part on the effect sizes observed by Lang et al (42), who enrolled 24 healthy subjects in 6 groups involving a cross over between manual, low-frequency and high-frequency acupuncture and were able to observe significant differences in QST (CDT) between the 3 acupuncture modalities, $p=0.0034$. In our current study, the cross-over design is based on the comparisons of Median and Ulnar nerves; however, the individual methods of acupuncture will be populated by different cohorts. For this reason, the random-effects blocking of our mixed- models will have the nerve dependence

grouped by subject but the modality contrasts will be inter-subject and not require a serial correlation correction. With a significant difference observed by Lang et al with groups of n=6, the proposed sample size of 20 per intervention group should be more than sufficient to observe differences among the modalities, even without the explicit cross-over design. Please see statistical analysis plan for further details.

As the goal is to recruit 20 subjects per arm, for a total of 60 study completers, we anticipate the need to screen and enroll approximately 75 subjects, including with baseline nerve conduction studies to confirm the diagnosis of mild-moderate CTS and assure that the electrodiagnostic inclusion criteria for this study are met.

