2.6. Quantitative Sensation Testing (QST)

Computer-assisted Sensory Evaluation (CASE) aka Quantitative Sensation Testing (QST) has been in clinical use since the late 1970s, when Dyck, O'Brien et al introduced the concept of an automated system to evaluate touch-pressure vibration and thermal cutaneous sensation (38). QST is administered in a lab and consists of standardized, precisely delivered computer-generated stimuli, based on careful study of physiologic perception thresholds and “just noticeable difference (JND)” of heat, cold, vibration and touch-pressure (39). Typically the lateral side of the nail bed is used to assess vibration detection threshold (VDT) in the hand and the dorsal surface of the hand is used to assess cooling (CDT) or heating detection threshold.

Fig.2. CASE IV Vibration Stimulator

[figure not shown]

[figure not shown]
Fig.3. CASE IV Thermal Stimulator

The creators of the CASE system created various algorithms for assessing hyper- and hypoalgesia in peripheral neuropathy patients. QST performed with the fourth generation system (CASEIV) have been shown to be efficient, reproducible, and validated against other algorithms of sensory testing (40). The correlation coefficients for vibratory detection threshold (VDT) and cooling detection threshold (CDT) have been found by greater than 0.9 (40). While QST has become a widely-used research tool, the validity of its results is highly dependent on the subject's ability to cooperate and sustain focused attention on stimulus presentation. Therefore, QST cannot be administered when the patient is inattentive, uncooperative, demented, sedated, or too ill to cooperate.

2.7. Study Rationale - Acupuncture for Carpal Tunnel Syndrome, PC6 and the Median Nerve

One area of acupuncture research, which has yielded successful results, is the efficacy of acupuncture in the treatment of Carpal Tunnel Syndrome (CTS). Acupuncture has shown to be effective for mild-moderate CTS with lasting effects on Nerve Conduction Studies (NCS) a year post-treatment (21). Additionally, laser acupuncture and TENS applied to the wrist has been shown to be effective in the treatment of CTS, with symptom improvement still present on 1-3 year follow-up (22, 23). Interestingly the above treatment protocols all involved acupuncture regimens with needles placed in the Pericardium channel (PC), most commonly PC6 (21, 24) and PC7 (21, 22, 23, 25) and PC3 (25), see **Figure 4** below.

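### The 80% power claimed for a 0.35°C change in cold detection threshold with 20 subjects per arm does not follow from the stated variance; a two-sided paired t-test on those inputs has about 43%.

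*Combined protocol and SAP*

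**What the plan says.** Section 9.1 (Sample Size Calculation) bases the CDT calculation on a cited study of acupuncture in healthy volunteers. It "assumed the variance of the change in QST outcomes due to local acupuncture delivery over the Median and Ulnar nerves will be comparable" with what that study found, and puts the value at 0.696 (°C)². It then takes "a minimum QST change of 0.35°C" as the effect to detect and states that this would be significant at alpha 0.05 "with 80% power with 20 subjects per arm". Neither the test nor its sidedness is named. From the same study it quotes CDT values before and after low-frequency acupuncture of -3.6 ± 0.9°C and -3.4 ± 0.4°C.

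Two later statements in 9.1 rely on this arm size. For Aim 1: "Specific Aim 1: We expect that the proposed sample size of 20 per acupuncture modality will enable us to see significant treatment-dependent changes". That statement concerns the median nerve, within each of the three modalities. For Aim 2: "the proposed sample size from Specific Aim 1 (20 subjects per acupuncture modality) is expected to be sufficient for these comparisons".

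Section 9.1 also gives a parallel calculation for median motor nerve conduction velocity (NCV): a change of 3.7 m/s, described as 8% of a mean of 47.5 m/s, with SD 5.76 m/s, and the same arm size, alpha and power.

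**The concern.** Both calculations in 9.1 claim 80% power at the same alpha with the same 20 subjects, but their standardised effects differ widely: 0.35/0.834 = 0.42 for CDT and 3.7/5.76 = 0.64 for NCV. One test at one sample size cannot have 80% power for both.

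CDT is the only sensory-testing outcome with a power calculation; vibration threshold has none. If the CDT figure is wrong, the expectation of significant sensory changes within each modality (Aim 1), and the reuse of that sample size for Aim 2, lose their stated support. On the plan's own inputs, an arm would miss a true 0.35°C change more often than detect it. A reader who trusts the 80% could then take a non-significant CDT result as evidence of no effect.

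**Working it through.** **Inputs, all from section 9.1.** Change to detect 0.35°C; variance of the change 0.696 (°C)²; n = 20 per arm; alpha 0.05; claimed power 80%. For NCV: change 3.7 m/s, SD 5.76 m/s, same n, alpha and power.

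**Formula.** The stated variance is that of the change and the Aim 1 claim is within one modality, so the matching test is a one-sample (paired) t-test on the changes. With noncentrality λ = (δ/σ)√n and n − 1 = 19 degrees of freedom, two-sided power is P(|T| > 2.093), where T is noncentral t with noncentrality λ. The one-sided cut-off is 1.729.

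**Does this formula reproduce the plan's other figure?** For NCV, δ/σ = 3.7/5.76 = 0.642 and power is 77.8% (81.9% by the normal approximation, which returns n = 20 for 80%). With 8% of 47.5 = 3.8 m/s, power is 79.9%. This is close enough to suggest the formula used. It says nothing about whether 5.76 m/s is the right SD for a change in NCV.

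**The same formula for CDT.** σ = √0.696 = 0.834°C; δ/σ = 0.35/0.834 = 0.4195; λ = 0.4195 × √20 = 1.876. Power is **42.9% two-sided** and 56.5% one-sided.

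- 80% power at n = 20, two-sided, needs δ/σ = 0.660. The detectable change is 0.660 × 0.834 = 0.55°C (one-sided 0.48°C).
- 80% power for 0.35°C at this variance needs n = 47 (one-sided 37).
- 80% power for 0.35°C at n = 20 needs an SD of the change of about 0.53°C, variance 0.28 (one-sided 0.61°C, variance 0.37).

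**Other tests on the same inputs, n = 20.** Normal approximation: 46.7% two-sided, 59.2% one-sided. Two independent groups of 20, t-test: 25.3% two-sided, 36.6% one-sided. None comes near 80%.

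**Where 0.696 may come from (inference only).** Pooling the two quoted SDs gives √((0.9² + 0.4²)/2) = √0.485 = 0.696. The number labelled a variance therefore equals a pooled SD; the pooled variance would be 0.485. Even so, a pooled SD of before and after values is not the SD of the change, which also depends on the before/after correlation r.

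**Power for 0.35°C at n = 20 under other readings:**

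| Reading | Two-sided | One-sided |
|---|---|---|
| 0.696 is the variance of the change (as written) | 43% | 57% |
| 0.696 is the SD of the change | 57% | 70% |
| SDs 0.9 and 0.4, variance of change 0.97 − 0.72r: r = 0 | 33% | 46% |
| same, r = 0.5 | 48% | 61% |
| same, r = 0.8 | 66% | 78% |
| same, r = 0.9 | 74% | 84% |
| 0.696 is the variance at each time point, variance of change 1.392(1 − r): r = 0.5 | 43% | 57% |
| same, r = 0.7 | 63% | 75% |
| same, r = 0.8 | 80% | 89% |
| same, r = 0.9 | 98% | 99% |

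With the quoted SDs of 0.9 and 0.4, 80% power needs r of about 0.957 two-sided or about 0.84 one-sided. The values of r are assumptions, because 9.1 gives none.

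**The case against.** The strongest reply is that 43% needs a test and a sidedness that 9.1 does not give, and that some readings do reach 80%. The Aim 1 hypothesis is directional, so a one-sided test is conceivable. The source variance is described in terms of sensory values after acupuncture, so 0.696 might be a variance at one time point. Section 2.6 also says: "The correlation coefficients for vibratory detection threshold (VDT) and cooling detection threshold (CDT) have been found by greater than 0.9". With correlations that high, power would be 98% if 0.696 is the variance at each time point. With the quoted SDs and a one-sided test it would be 84% at r = 0.9.

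This shows that the claim might be defensible on inputs the plan does not state. It does not rescue the claim as written. Section 9.1 assigns 0.696 to the variance of the change, which already absorbs any correlation, and one-sided testing then gives only 57%. Section 2.6 does not tie its coefficients to values before and after acupuncture, and 9.1 does not use them.

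Three further points are fair, but do not change the result.

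- **Planned model.** Section 9.4 plans a mixed model with age and gender covariates, and the Data Form averages three CDT readings per nerve. Either might reduce residual variance, but neither is quantified. Borrowing error degrees of freedom across arms (57 in place of 19) lifts power only from 43% to about 45%.
- **Pooling.** Section 9.3 describes a pooled median/ulnar comparison for Aim 2. At the stated variance, a single change pooled over 60 subjects has about 89% power, and an independent-samples comparison with 60 values per nerve about 63%. However, the claims in 9.1 are per arm and within each modality.
- **Pilot status.** The study is a pilot with exploratory, unadjusted analyses, and the NCV calculation is a separate argument for 20 per arm. That limits the consequences but does not make the CDT figure correct.

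**Conclusion.** The concern holds. On the inputs in section 9.1, power for a 0.35°C change in CDT with 20 subjects is about 43%, not 80%, and the change detectable with 80% power is about 0.55°C. This assumes a two-sided paired t-test, which is the test that fits the variance as described and nearly returns the NCV figure. With a one-sided test the values are 57% and 0.48°C. Relabelling 0.696 as the SD of the change still leaves 57% two-sided and 70% one-sided.

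That 0.696 is a mislabelled pooled SD is plausible from the arithmetic but can be settled only from the source study; the conclusion does not depend on it. Aim 1 and Aim 2 are affected because their statements reuse the arm size. Aim 3 rests on this calculation only in part.

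**What to change.** In section 9.1:

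1. Confirm from the source what 0.696 is and in what unit.
2. State the SD of the change actually assumed, with any before/after correlation used to derive it and where that correlation comes from. Do not enter 0.696 as the SD of the change unless the source supports it.
3. Name the test and its sidedness.
4. Replace the 80% statement for 0.35°C with the figure those inputs give.

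If the stated variance stands and the test is two-sided, suitable text would be: *With 20 subjects per arm, a two-sided paired t-test at alpha 0.05 and a variance of the change of 0.696 (°C)² has 80% power for a CDT change of about 0.55°C; power for 0.35°C is about 43%.*

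Carry the corrected figure into the Aim 1 sample-size statement and the Aim 2 statement that reuses it.

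The cost is a rewording of 9.1. No extra subjects are needed, and endpoints and analysis stay as they are. If the stated variance stands, the plan must report either a lower power or a larger detectable change.

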9.4. Statistical Analysis Plan

Primary statistical analysis for all 3 Specific Aims will use linear mixed-effect models to evaluate the effects of treatment group and intervened nerve location on the outcome measures described above. A mixed-model design will be used to create an intention-to-treat framework

and allow for any missing data. Principal assessment will be on the change in outcomes resulting from acupuncture intervention, calculated as the difference in outcomes before and after treatment. These outcomes will include CDT and VDT, distal motor/sensory latencies, CMAP and SNAP amplitudes, CMAP area and duration, nerve conduction velocities (Specific Aim 1). Acupuncture characterization will be carried out first in the Median and Ulnar nerves of the arm (Specific Aims 1, 2). In both Median and Ulnar nerve interventions, group will be a three level factor based on the type of acupuncture - MA, LF-EA and HF-EA (Specific Aim 3).

Specific Aims 1 and 2:

As a principal independent variable, location of the intervention will be a four-level factor encompassing the possible combinations of treated and evaluated nerves. For Specific Aims 1 and 2, these levels will be: MM – Median treated and tested, MU – Median treated and Ulnar tested, UM – Ulnar treated and Median tested, and UU – Ulnar treated and tested. A time variable (Week 1, Week 2) will also be included to test for any effects due to order of the treated nerves. Additional covariates known to be associated with QST and NCS outcomes such as age and gender will be corrected for as well. Secondary analysis will include treatment evaluations of outcomes within each location of intervention and additional contrasts between the four time points (pre and post treatment for both Week 1 and Week 2). Persistence of the acupuncture effects will specifically be assessed by comparing changes in outcomes after the first treatment but before the second session.

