Another way to characterize the wash-out effect of acupuncture is to compare baseline data from Week 1 and Week 2. We will perform an exploratory analysis to assess for an interaction between location and time, in a mixed linear model. We will incorporate nerve location, evaluation time and the location-time interaction to check for dependencies between Week 1 and Week 2. As stated, the dependent outcomes of all models are the change in QST and NCS from baseline to post-acupuncture. This will allow for a full assessment of washout and carry-over effects with respect both to the nerve location (healthy Ulnar vs diseased Median), time (Week 1 vs Week 2) as well as the order of nerve assessment (the interaction). However, with the repeated nerve measures, it will still be necessary to utilize a mixed-model approach so that the random-effects blocking (nerve location dependent on subject) will allow for the intra-subject serial correlation. For the final model, although exploration of the wash-out effect will be critical, it will pose to be impractical to keep all these covariates in the final model. Only significant time-dependent interactions will be included since the model would otherwise suffer from overfitting due to too many covariates and the limited sample size.

Specific Aim 2: Following completion of Specific Aim 1, we expect to see significant acupuncture effect on the Median nerve (within each acupuncture group). In our proposed mixed linear model for Specific Aims 1 and 2 this would represent MM on the level of each individual group (MA, LF-EA, HF-EA). Conversely, we do not expect to observe a significant effect of acupuncture on the healthy Ulnar nerve as it is already functioning at optimal physiologic level. This would be the UU at the level of each individual group and corresponds to a clinical control. We will conduct direct contrasts between MM and UU as part of the mixed linear model with nerve location, time dependencies and random-effects grouping following the same design as in Specific Aim 1.

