Specific Aim 3: We will revise the linear mixed model and focus on the MM factor from Specific Aims 1 and 2 (Median nerve treated and tested). In this revised model we will incorporate acupuncture modality as a 3-factor covariate (MA, LF-EA, HF-EA). Incorporating both the 4-factor sets of nerve intervention/assessment combinations and the 3-factor acupuncture modality would create a very complex model with over 15 variables. As described in the washout analysis, this will lead to overfitting of the model and cause it to be underpowered at 60 subjects. We could run a similar revised mixed liner model analysis substituting UU, UM or MU for MM, although this would be beyond the scope of Specific Aim 3.

Because of the exploratory nature of our analyses, no adjustment for multiple testing will be undertaken. Raw *P* values 0.05 will be regarded as statistically significant. Regardless, the multiple assessments inherent in the exploratory analysis will be discussed in future publications. Statistical analysis will be performed using SAS 9.1 (SAS Institute, Cary, NC).

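### Section 9.1 expects a significant median-nerve change in each of three modalities, but its own inputs give about 47% (NCV) and 8% (CDT) for all three together, and 9.4 states no contrast for that test.

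*Combined protocol and SAP*

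**What the plan says.** **Section 9.1.** For CDT the plan takes "a minimum QST change of 0.35°C" with a variance of 0.696, and claims detection at a "significance level of $\alpha=0.05$ with 80% power with 20 subjects per arm". For median motor NCV it takes 3.7 m/s, described as an 8% change from a mean of 47.5 with SD 5.76, at the "same arm size of 20 subjects and at the same significance of $\alpha=0.05$ and 80% power". Under Specific Aim 1 it then expects 20 per modality to reveal "significant treatment-dependent changes in the NCS and QST (CDT, VDT) of the diseased Median nerve within each of the 3 intervention systems". Under Specific Aim 3 it states that the modalities are given to different subjects.

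**Section 9.4.** The opening says that the primary mixed models for all three aims assess treatment group and treated-nerve location, and it defines a three-level group factor that it tags to Aim 3. For Aims 1 and 2 the listed terms are these: "location of the intervention will be a four-level factor encompassing the possible combinations of treated and evaluated nerves" (MM, MU, UM, UU), then week, age and gender. Modality is not among them. Under Aim 2 the text says "we expect to see significant acupuncture effect on the Median nerve (within each acupuncture group"), and identifies this with the MM level (median treated and tested) of the Aims 1 and 2 model, taken separately in each modality. Under Aim 3, modality enters a revised model restricted to MM. Combining the four location levels with the three modalities is declined there as too complex for 60 subjects. No adjustment for multiple testing is planned.

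**The concern.** A power of 80% for one test in one arm does not carry over to a result expected in three arms at once. The Aim 1 expectation is of that joint kind, it spans several outcomes, and it includes one outcome (VDT) for which 9.1 gives neither an effect nor a variance.

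The test that the sample size is built on, the MM change within one modality, also needs a model and a contrast. A model with location but no modality returns one MM effect, not three.

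What is at stake is interpretation. If some arms cross p=0.05 and others do not, a reader may take that as evidence that the modalities differ, which is the Aim 3 hypothesis. Such a pattern is a likely product of limited power even when all three modalities work equally well. Meanwhile the estimate that 60 subjects can support best, MM averaged over the arms, is never named as the Aim 1 test.

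**Working it through.** **Inputs, all from section 9.1.** CDT change 0.35 °C with variance 0.696, so SD = √0.696 = 0.834. NCV change 3.7 m/s, SD 5.76 (variance 33.2). n = 20 per arm, alpha 0.05. Sidedness is not stated; 9.4 says only that raw p values at 0.05 "will be regarded as statistically significant". I take tests as two-sided and show one-sided results as a range.

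**Method.** One-sample t test on the pre-to-post change in one arm. Power comes from the noncentral t distribution with n−1 degrees of freedom and noncentrality (change/SD) × √n. The two-sided critical value at n=20 is 2.093.

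**Reproducing the stated 80% per arm**

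| Outcome | Noncentrality | Two-sided t | Two-sided normal approx. | One-sided t |
|---|---|---|---|---|
| NCV 3.7 m/s | 3.7/5.76 × √20 = 2.87 | 77.8% | 81.9% | 86.9% |
| CDT 0.35 °C | 0.35/0.834 × √20 = 1.88 | 42.9% | 46.7% | 56.5% |

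NCV reproduces, near enough. With a full 8% (0.08 × 47.5 = 3.8 m/s) the t test gives 79.9%. CDT does not reproduce. Reading 0.696 as an SD gives 56.9% (two-sided t) and at most 72.7% (one-sided, normal approximation). A two-sample comparison of 20 with 20 gives about 25%. CDT at 0.35 °C needs about 47 per arm for 80% (two-sided t). With 20 per arm the detectable change is 0.660 × 0.834 = 0.55 °C.

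**All three arms.** The arms hold different subjects, so for one outcome the probabilities multiply.

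| Per-arm power | All three | One or two | None |
|---|---|---|---|
| Nominal 80% | 0.8³ = 51.2% | 3(0.8²)(0.2) + 3(0.8)(0.2²) = 48.0% | 0.2³ = 0.8% |
| NCV 77.8% | 47.1% | 51.8% | 1.1% |
| CDT 42.9% | 7.9% | 73.5% | 18.6% |

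With one-sided t tests the all-three figures are 0.869³ = 66% for NCV and 0.565³ = 18% for CDT. A joint 80% needs 0.8^(1/3) = 92.8% per arm. By two-sided t that is about 31 per arm for NCV and 69 for CDT.

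**Several outcomes.** Requiring CDT, VDT and one NCS measure in all three arms, each at a nominal 80%, gives 0.8⁹ = 13% if the outcomes are independent and 51% if perfectly correlated. The plan gives no correlation, so only this range can be stated.

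**Averaging MM over the three arms (n=60, two-sided t).** Noncentrality for CDT is 0.35/0.834 × √60 = 3.25, which gives 89% power. Detectable changes at 80% power are 0.3677 × 0.834 = 0.31 °C and 0.3677 × 5.76 = 2.1 m/s. Adding modality to the model leaves 57 rather than 59 degrees of freedom, and the 89% is unchanged. If only one modality works at 0.35 °C, the average is 0.35/3 = 0.117 °C and power is about 19%.

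**The model text in 9.4.** Four statements do not fit together: a primary analysis that names treatment group; an Aims 1 and 2 term list without it; an Aim 2 paragraph that reads MM by modality from that model; and an Aim 3 paragraph that declines to put location and modality together. The MM-only model under Aim 3 could yield three arm-specific means, but it is assigned to comparing modalities.

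**The case against.** The strongest reply is that this is a pilot with analyses declared exploratory, that powering each comparison separately is ordinary practice, and that 9.1 states an expectation, not a promise. Nowhere does the plan make success depend on all three arms, or present 80% as a joint figure. That stands, and it means that modest joint power is not in itself a fault. It does not rescue a stated CDT power that its own inputs do not give, or a VDT claim with no inputs.

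A second reply is that modality is not absent. The opening of 9.4 names treatment group, 9.1 plans the median-ulnar comparisons separately by modality, and the Aim 3 model includes modality. This also stands. The accurate complaint is inconsistency and an unstated contrast, not omission.

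Three stronger readings should be resisted:

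- A reader might infer that 9.4 demotes the within-modality test to secondary status. The sentence in question, "Secondary analysis will include treatment evaluations of outcomes within each location of intervention", concerns location and says nothing about modality.
- A reader might infer that a mixed pattern is the most likely result on the plan's nominal power. On one outcome at 80% per arm it is 48%, against 51% for all three. It becomes the likeliest on the plan's CDT inputs (73%), and narrowly on NCV by the t test (52%).
- A reader might take 51% as the joint figure to write into the protocol. It would be wrong for CDT, where the plan's inputs give 8%.

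Making the average over arms the Aim 1 test does change what is estimated. That is a choice for the investigators, with the cost given under the fix.

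**Conclusion.** The point holds in two parts.

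First, the Aim 1 expectation goes beyond its power basis. At a nominal 80% the chance of significance in all three arms is 51% on one outcome. On the plan's own inputs it is about 47% for NCV and 8% for CDT, with per-arm power of about 78% and 43%. VDT cannot be assessed.

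Second, 9.4 specifies no contrast that delivers the within-modality median test, because its statements on modality conflict.

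The figures assume a two-sided one-sample t test, 20 analysed per arm, equal true effects in all arms, and the plan's variances taken as variances of change. The NCV variance is a between-patient figure that the plan carries over to the change. A smaller variance of change, one-sided testing or larger effects would raise the probabilities; requiring several outcomes together would lower them. One-sided testing does not restore 80% for CDT. The inconsistency in 9.4 depends on none of these assumptions.

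**What to change.** **Section 9.1.** State that power is per test and per arm. Replace the CDT claim with about 43% at 0.35 °C, or a detectable change of about 0.55 °C with 20 per arm. State whether tests are two-sided. Give the probability that all three arms are significant, by outcome (about 47% for NCV and 8% for CDT). Drop VDT from the expectation, or give its effect size and variance.

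**Section 9.4.** Reconcile the Aim 1 and Aim 2 text of 9.1 with the opening, the Aims 1 and 2 term list, the Aim 2 paragraph and the Aim 3 paragraph of 9.4. Name the MM change averaged over the three arms (n=60) as the Aim 1 test, from a model that includes modality. Report the three modality-specific MM changes with confidence intervals, and say that significance in one arm but not another will not be read as a difference between modalities; that question belongs to the Aim 3 comparison.

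**Cost.** Wording in 9.1 and one specified model and contrast in 9.4. No change to subjects, visits or procedures. The downside is dilution: if only one modality works at 0.35 °C, the averaged test has about 19% power, so the modality-specific estimates must stay in the report.
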